## STATEMENT OF COMPLIANCE

The trial will be conducted in accordance with International Conference on Harmonization Good Clinical Practice (ICH GCP) and applicable United States (US) Code of Federal Regulations (CFR). The Principal Investigator will assure that no deviation from, or changes to the protocol will take place without prior agreement from the Investigational New Drug (IND) sponsor, funding agency and documented approval from the Institutional Review Board (IRB), except where necessary to eliminate an immediate hazard(s) to the trial participants. All personnel involved in the conduct of this study have completed Human Subjects Protection and ICH GCP Training.

The protocol, informed consent forms, recruitment materials, and all participant materials will be submitted to the IRB for review and approval. Approval of both the protocol and the consent form must be obtained before any participant is enrolled. Any amendment to the protocol will require review and approval by the IRB before the changes are implemented to the study. All changes to the consent form will be IRB approved; a determination will be made regarding whether a new consent needs to be obtained from participants who provided consent, using a previously approved consent form.

**[name] MD, Principal Investigator**

## LIST OF ABBREVIATIONS

AE	adverse event
AST	Aspartate aminotransferase
ALT	Alanine aminotransferase
BUN	blood urea nitrogen
CRF	case report form
CSF	cerebrospinal fluid
CT	computed tomography
DCI	delayed cerebral ischemia
DDI	drug drug interaction
DHET	dihydroxyeicosatrienoic acids
DPOME	dihydroxyoctadec-12-enoic acid
ECG	electrocardiogram
eCRF	electronic case report form
EETs	epoxyeicosatrienoic acids
EF	ejection fraction
EMR	electronic medical record
EPOME	epoxyoctadecenoic acid
EVD	external ventricular drain
FDA	food and drug administration
GCP	good clinical practice
GLP	good laboratory practice
GMP	good manufacturing practice
GOSE	Extended Glasgow Outcome Scale
HDL	high density lipoprotein
ICH	International Conference on Harmonization
IND	Investigational New Drug
IRB	Institutional Review board
LAR	legally authorized representative
LDL	low density lipoprotein
LV	left ventricle
MCA	middle cerebral artery
MOP	manual of procedures
MR	magnetic resonance
mRS	modified Rankin scale
NSICU	Neurosciences Intensive Care Unit
NSTEMI	non-ST elevation myocardial infarction
OHRP	office for human research protections
OHSU	Oregon Health and Science University
PCP	primary care provider
PI	principal investigator
QC	quality control
SAE	serious adverse event
SAH	subarachnoid hemorrhage
sEH	soluble epoxide hydrolase
SOA	Schedule of activities
SOP	standard operating procedure
STEMI	ST elevation myocardial infarction
UP	unanticipated problem
US	United States

## 1 PROTOCOL SUMMARY

### 1.1 SYNOPSIS

Title:	Subarachnoid hemorrhage and soluble epoxide hydrolase inhibition: a phase 1b trial
Study Description:	Soluble epoxide hydrolase (sEH) is the metabolizing enzyme of epoxyeicosatrienoic acids (EETs), which may play a role in reducing neuroinflammation and regulating cerebral blood flow after subarachnoid hemorrhage (SAH). We hypothesize that pharmacologic inhibition of the sEH enzyme is safe and will result in increased EETs availability at the neurovascular unit, and a measured increase in the EET/DHET ratio in the serum and cerebrospinal fluid. This study is a double-blind, placebo-controlled, phase 1b randomized trial to evaluate the safety and of GSK2256294, an inhibitor of soluble epoxide hydrolase, in patients with aneurysmal SAH.
Objectives:	Primary Objective: Determine the safety of administration of GSK2256294 in patients with aneurysmal SAH. Secondary Objective: Determine the pharmacodynamics effect of administration of GSK2256294 in patients with aneurysmal SAH on reducing EETs metabolism and biomarkers of cerebrovascular inflammation and endothelial injury. Tertiary Objective: Provide preliminary estimates of clinical endpoints to inform the design of a larger trial
Endpoints:	Primary Endpoints: Determination of safety Secondary endpoints: 

1. Study days 7 and 10 serum EET/DHET ratios

2. Study days 7 and 10 cerebrospinal fluid (CSF) EET/DHET ratios

3. Study days 7 and 10 serum EPOME/DPOME ratios

4. Neuroinflammatory and endothelial injury biomarker levels from the blood and CSF at day 7 and day 10.

 Tertiary, exploratory endpoints: Clinical outcomes associated with SAH including neurologic status, disposition, vital status and incidence of delayed cerebral ischemia.  Up to 30 subjects will be randomized. Patients age 18 or above with confirmed ruptured will be approached to provide written informed consent. In order to be eligible to participate in this study, an individual must meet all of the following criteria: non-contrast CT with evidence of subarachnoid hemorrhage, and digital subtraction cerebral angiography or CT angiogram documenting the presence of

a cerebral aneurysm. An individual who meets any of the following criteria will be excluded from participation in this study: evidence of prolonged QTc >500 milliseconds, baseline AST and ALT > 2x normal reference values, administration of strong inducers/inhibitors of CYP3A4, symptom onset compatible with SAH of  $\geq 3$  days prior to admission to Oregon Health and Science University Neurosciences Intensive Care Unit (OHSU NSICU), unable to speak or understand English or Spanish, current pregnancy based on urine HCG positive pregnancy test, preexisting severe neurologic deficit or condition, chronic renal failure requiring dialysis, severe terminal disease with life expectancy <6 months, or refusal of informed consent.

**Phase:**

Phase 1B

**Description of Sites/Facilities Enrolling Participants:**

The study will take place at Oregon Health & Science University Hospital, with enrollment of patients admitted to the OHSU NSICU, a part of a comprehensive stroke center certified by the American Heart Association and Joint Commission for Accreditation of Healthcare Organizations, with a catchment area including the state of Oregon, Southwest Washington and Northern California. Approximately 80-100 patients with aneurysmal SAH are admitted each year.

**Description of Study Intervention:**

Up to 30 patients will be equally randomized to receive once daily either 10 mg dose of GSK2256294 or placebo enterally for a duration of 10 days.

**Study Duration:**

[figure not shown]
24 months

**Participant Duration:**

90 days

## 2 INTRODUCTION

### 2.1 STUDY RATIONALE

SAH due to the rupture of an intracranial aneurysm is a life threatening medical emergency with a mortality of 25-40%. In survivors of the initial bleeding, endothelial injury and blood in the subarachnoid space induce an intense inflammatory response, leading to vessel wall thickening and caliber reduction over the first 10-14 days following the bleed. This inflammatory process may cause delayed cerebral ischemia (DCI). DCI is the clinical result of a complex neurovascular inflammatory response characterized by blood brain barrier breakdown, impaired blood vessel autoregulation, direct inflammatory injury, thrombosis, and cerebral edema. The ultimate result is decreased cerebral blood flow and altered neurovascular communications. The inflammatory and ischemic injury associated with DCI may result in long-term cognitive dysfunction and functional disability in >50% of survivors.

In an effort to prevent and treat DCI, patients with SAH require intensive care unit monitoring of hemodynamics and neurologic function for 10-14 days after the primary hemorrhage. Monitoring of the tone of intracranial blood vessels is routinely carried out daily with transcranial Doppler flow velocities, and cerebral angiography when indicated. Clinical deteriorations that are accompanied by signs of decreased cerebral blood flow are treated with blood pressure augmentation and/or intra-arterial vasodilators, with limited therapeutic effectiveness. The only recommended pharmacological therapy is the prophylactic administration of a 21-day course of the calcium channel blocker nimodipine.[1] There are currently no other effective therapies to directly target microvascular blood vessel dysregulation or neuroinflammation.

### 2.2 BACKGROUND

Epoxyeicosatrienoic acids (EETs) are arachidonic acid metabolites that are emerging as important regulators of cerebral blood flow and neuroinflammation after brain injury, including SAH.[2, 3] EETs are synthesized by cytochrome P450 epoxygenases in response to cellular insults including ischemia. The beneficial properties of EETs, which have been demonstrated *in vitro* and *in vivo*, include: vasodilation, promotion of angiogenesis, reduced microvascular thrombosis, inhibition of platelet aggregation, decreased apoptosis, and decreased inflammation. All these processes are disturbed following SAH. EETs have multiple sites of action: on the endothelium where they likely regulate inflammatory response, on vascular smooth muscle where they are involved in regulating vasomotor tone, and more broadly throughout the neurovascular units regulating neurovascular communication.

Multiple biomarkers have been identified that characterize neuroinflammation after SAH, and many have been associated with EETs signaling (Table 1). EETs are primarily metabolized to inactive dihydroxyeicosatrienoic acids (DHETs) by the enzyme soluble epoxide hydrolase (sEH), which is expressed in cerebral endothelial and smooth muscle cells as well as astrocyte cell bodies and foot processes.[4]

Several polymorphisms in the gene responsible for sEH transcription, designated EPHX2, alter the structure and function of the enzyme.[5, 6] One variant conferring increased sEH activity and inactivation of EETs, known as K55R, has been linked to hypertension, ischemic stroke and coronary artery disease.[7-9] In patients with SAH, K55R genotype sEH is associated with

increased mortality and incidence of stroke.[10] Conversely, pharmacologic inhibition of sEH reduces infarct size after transient cerebral ischemia in animal models.[11]

Inhibition of sEH in humans has recently become feasible due to the availability of a drug under development by GlaxoSmithKline, GSK2256294.

### **Pharmacokinetics and product metabolism**

In human and animal studies, the oral bioavailability of GSK2256294 was generally high, indicating good absorption, low plasma clearance and a half-life of 20-30 hours. Steady state was achieved within 6-8 days after daily repeat dosing in humans.[12] GSK2256294 has low to moderate protein binding, high passive permeability, and a moderate volume of distribution. Structural information on GSK2256294 metabolism in humans following both single and repeat oral doses in both healthy volunteers and obese smokers indicated GSK2256294 was the major drug related component in human plasma with biliary and urinary metabolites being formed by either oxidation with or without subsequent glucuronidation and N-demethylation. Similar metabolites were detected in human and nonclinical hepatocytes.

In vitro data indicated limited potential for GSK2256294 to be a perpetrator of cytochrome P450-mediated drug interactions. Population-based physiologically based pharmacokinetics model simulations, evaluating the risk of an interaction between GSK2256294 and a strong CYP3A4 inhibitor, predicted a moderate increase (3.2 fold) to the mean systemic exposure of GSK2256294 when administered together. Co-administration of strong inhibitors and inducers of CYP3A4 has been recommended to be prohibited.

GSK2256294 inhibited the human breast cancer resistance protein and organic anion transporting polypeptide 1B1 in vitro, suggesting the potential for drug interactions with statins that have their disposition modulated by these transporters. However, a physiologically based pharmacokinetic population based drug-drug interaction modelling simulation between GSK2256294 and sensitive substrates (including rosuvastatin) has predicted the clinical interaction risk to be negligible (<1.05 fold). Hence monitoring of adverse events is recommended with the concomitant use of GSK2256294 with statins.

### **Toxicology**

Administration of GSK2256294 was well tolerated at doses up to 600 mg/kg/day in the rat and 1000 mg/kg/day in the monkey. A dose of 1000 mg/kg/day in the rat was generally less tolerated, with adverse clinical signs of reduced food consumption and body weight loss along with macroscopic and microscopic gastric and renal changes and urinalysis effects. In addition, increased liver weight and hepatocyte hypertrophy at 1000 mg/kg/day were noted in rats, along with associated thyroid follicular cell hypertrophy, effects which are often secondary to drug metabolizing enzyme induction in rats (systemic exposure was also reduced at Days 14 and 28 in rat as compared to Day 1). Minimal to mild atrophy of mammary glands was also seen in male rats at 1000 mg/kg/day. At >100 mg/kg/day in rats, there were increased serum cholesterol concentrations along with elevated high-density lipoprotein (HDL) and low-density lipoprotein (LDL) fractions. These were considered non-adverse. GSK2256294 was negative in a battery of genotoxicity assays.

In reproductive and developmental toxicity studies to date, assessment of male rat fertility in 13 week studies has identified no test article-related effects on male mating, fertility or male mediated fetal developmental toxicity after 2 and 11 weeks of dosing at up to 1000 mg/kg/day.

### **Human Studies**

The pharmacokinetics, pharmacodynamics and safety of GSK2256294 has been evaluated in three Phase I studies: an ascending single and repeat dose study of GSK2256294 in healthy male volunteers and otherwise healthy adult male overweight and moderately obese smokers, a single dose study in healthy young and elderly subjects, and a repeat dose study in healthy volunteers. When administered with food (high fat meal), there was, on average, a 22% increase in AUC of GSK2256294 with similar maximum plasma concentration. The median time to peak concentration was delayed by approximately 2 hours when GSK2256294 was administered with food (3.0 hrs versus 1.0 hr). These differences were not deemed to be clinically significant and GSK2256294 can be administered without any meal restrictions in future clinical studies.

GSK2256294 was eliminated mainly by direct biliary secretion and metabolism with metabolites being excreted in both urine and bile. Renal elimination of unchanged parent represented <5% of the dose. In the single dose cohorts AE reporting was higher following GSK2256294 than placebo, but there was no evidence of increased reporting with increased dose.

### **Pharmacodynamics and Dose Finding**

The inhibitory effect of GSK2256294 on exogenous deuterium-labeled EETs was estimated in an ex vivo assay in healthy volunteers and otherwise healthy overweight to moderately obese smokers following single doses of 2-20mg, and following 14 days of once daily repeat dosing at 6mg and 18mg.[12] The sEH activity was evaluated by the formation of 14,15 dDHET, corrected for non-sEH mediated hydrolysis and subsequently the % inhibition of sEH activity was defined. >95% enzyme inhibition was observed for up to 48 hours following a single 10mg dose. >98% enzyme inhibition was observed to be sustained for up to 48 hours following 14 days of daily administration.

## **2.3 RISK/BENEFIT ASSESSMENT**

### **2.3.1 KNOWN POTENTIAL RISKS**

GSK2256294 has been studied in several clinical cohorts. The most commonly reported AEs in healthy volunteers were contact dermatitis and headache, and in healthy adult male overweight and moderately obese smokers were headache and fatigue. Most AEs were of mild or moderate intensity. In the repeat dose cohorts of healthy adult male overweight and moderately obese smokers, AE reporting was similar in frequency overall following repeat administration of GSK2256294 compared with placebo. The most frequently reported AEs were headache and nasopharyngitis. All AEs were considered to be of mild or moderate severity. There was one AE leading to withdrawal (presyncope) reported in healthy volunteers and one SAE in healthy adult male overweight and moderately obese smokers (nephrolithiasis) reported. Neither of these events were deemed likely to be related to the study drug.

Clinically significant abnormalities in clinical chemistry and hematology parameters were infrequent and most were present at baseline. Following repeat dosing with GSK2256294, there was a statistically significant decrease in HDL compared to baseline. The ratio to placebo of change from baseline in HDL was not statistically significant, though there was a trend for a dose-dependent difference. There were no changes in vital signs of clinical importance. A clinically significant abnormality (nodal rhythm) was reported for one subject with presyncope.

There were no fatal or non-fatal SAEs and no adverse event leading to the withdrawal. Treatment with GSK2256294 did not increase the room air pulmonary artery systolic pressure and did not augment the normal hypoxic pulmonary vasoconstrictive response in healthy subjects. No clinically significant changes in any of the clinical laboratory parameters, electrocardiograms (ECGs) and vital signs were observed.

GSK2256294 has been generally well tolerated in the clinic, although most studies with GSK2256294 have been of relatively short duration and the safety database is not extensive. Due to limited experience in human subjects, there is currently not enough information available about the relationship between administration of GSK2256294 and adverse events to assign causality. It is possible that there are other long-range risk associated with drug administration that have not been identified in previous trials.

No efficacy studies have been conducted to date. There is a potential that administration of the study drug will improve EETs signaling and reduce neuroinflammation and endothelial injury. Patients in the treatment group may experience less vasoconstriction, fewer delayed ischemic complications after SAH, and improved neurologic outcomes.

This study will also involve sample collection from the blood and CSF. Blood samples will be collected whenever possible from indwelling venous or arterial access. In the absence of an available access site, venipuncture will be performed by the bedside RN. CSF samples will be collected by accessing the EVD, which will have been placed as part of the patient's routine medical care for SAH. The EVD will be accessed in the same fashion as for routine, clinically-directed sampling, and wherever possible at the same time. EVD access may very slightly increase the risk of introduction of bacteria and the development of ventriculitis.

---

### 2.3.2 ASSESSMENT OF POTENTIAL RISKS AND BENEFITS

Based on previous phase 1 trials, the adverse event profile and pharmacologic interactions of GSK2256294 are minimal.[12] There is a lack of detailed, long-term event tracking, and this will be the first study of GSK2256294 in a critically ill patient population, so it is possible that there will be unanticipated adverse events. The drug exposure period will be relatively short, in line with previous phase 1 trials, and the monitoring will be significantly more intensive, which limits the additional risk.

In addition, patients admitted to the intensive care unit for the treatment of SAH will routinely undergo numerous blood draws, sampling of CSF and diagnostic procedures as part of the accepted standard of care. Our proposed study will not change the risks inherent to specimen sampling. Blood and CSF samples will be obtained at the same time (whenever feasible) and in the same fashion as routine and standard of care samples are obtained.

Study participation will not influence the clinical care of patients other than as defined in Section 11 within the Schedule of Activities. The potential benefit of reduced neuroinflammation and improved outcome in patients with an otherwise highly morbid, high mortality disease process outweighs these potential risks. Future patients with SAH may be benefited by the knowledge gained.

## 3 OBJECTIVES AND ENDPOINTS

- **Primary Objective:** Determine the safety of administration of GSK2256294 in patients with aneurysmal SAH.

Frequencies of AEs and SAEs: We will compare AEs and SAEs between the drug and placebo groups. We will also compare daily safety labs (serum sodium, blood glucose, blood urea nitrogen (BUN), creatinine, hematocrit, peripheral white blood cell count) between the groups. Specific to this patient population, we will also specifically screen for disease related events including seizure, new onset cardiomyopathy, NSTEMI/STEMI, hyponatremia, hospital acquired infection, mechanical ventilation, and thromboembolic events. We will describe the severity of headache (on a daily scale of 0-10).

**Justification:** Prior phase 1 studies of GSK2256294 have been in healthy volunteers with limited physiologic monitoring. The most common adverse event was headache. We will assess safety in this critically ill patient population with special focus on common sequelae of subarachnoid hemorrhage.

- **Secondary Objective:** Determine the pharmacodynamic effects of administration of GSK2256294 in patients with aneurysmal SAH.

To evaluate the effect of enzymatic inhibition on circulating EETs levels, we will measure day 7 and day 10 serum EET/DHET ratios. EETs levels will be measured using liquid chromatography and mass spectroscopy.

To evaluate the possible effect of enzymatic inhibition on CSF EETs levels we will measure day 7 and day 10 CSF EET/DHET ratios, and compare the drug and placebo groups. We will also measure other lipid metabolic substrates of sEH at days 7 and day 10, specifically serum epoxyoctadecenoic acid (EPOME) and dihydroxyoctadec-12-enoic acid (DPOME), to assess sEH enzyme activity.

To evaluate more downstream effects on measures of endothelial injury and neuroinflammation, we will measure multiple biomarkers in the blood and CSF at day 7 and day 10 (Table 1). The biomarkers chosen are surrogate endpoints representing pathways of the inflammatory cascade associated with clinical endpoints in SAH.

**Justification:** EETs are degraded to inactive byproducts DHETs by the enzyme sEH. sEH activity has previously been measured after exposure to the study drug, and found to reach steady state level of >95% drug inhibition at 7 days. Prior evaluations of drug efficacy have used indirect means to measure drug effectiveness in inhibiting exogenous EETs degradation. We will directly measure *in vivo* EETs levels after drug administration to determine the degree by which sEH inhibition results in measurable increases in systemic EETs. Endogenous EETs have a very short half-life and require rapid sample processing and meticulous storage conditions.

We have chosen to measure the EET/DHET ratio due to the normal fluctuations of EETs levels in the post-bleed period after SAH. The drug will be deemed effective if we measure higher EET/DHET ratio in the treatment group compared to placebo, i.e. higher EETs suggests decreased metabolism by sEH. It is possible that serum EET/DHET ratio will not be measurably increased. EETs have a very short serum half-life (minutes), and the most plausible site of action is at the neurovascular unit.

To more precisely estimate sEH enzyme activity in plasma, we will also measure the metabolism of more stable lipid substrates of sEH: EPOME, and the metabolic byproduct DPOME. Serum EPOME and DPOME levels have previously been used to measure the hydrolase activity of sEH.[13]

We will also determine whether there are CNS effects of the drug, either via direct measurement of increased EET/DHET ratio in the CSF, or via downstream effects on the inflammatory profile in the CSF and on the markers of endothelial dysfunction. This is particularly important because in healthy subjects and animals, the drug does not cross the blood brain barrier. It is possible that EETs have a localized action on the endothelium and vascular smooth muscle, without crossing the blood brain barrier. sEH inhibition may exert anti-inflammatory and vasodilatory effects at this site without changing measurable CSF EETs levels. If this is the case, we expect to detect differences in CSF inflammatory markers.

We anticipate a possible effect of the study drug in CSF for the following reasons: 1) There is breakdown of the blood brain barrier following SAH and both lipid and non-lipid soluble molecules may be able cross the neurovascular unit due to increased permeability; and 2) Endothelial-derived cytokines and mediators may be transported across compartments, including blood, perivascular space, and CSF. It will be important to confirm the site of action of the study drug is only at the endothelium level or if its effects on the central nervous system

We will collect biomarkers at multiple time points because eicosanoid levels, endothelial dysfunction, and the inflammatory response vary significantly over the natural course of subarachnoid hemorrhage. We may control for significant variations at baseline when interpreting the results.

- **Tertiary Objective:** Provide preliminary estimates of clinically relevant endpoints to inform the design of a larger trial.

We will collect clinical measurements on outcomes throughout the treatment course, at hospital discharge and at 90-day follow-up. To assess DCI directly, we will measure daily middle cerebral artery (MCA) transcranial Doppler flow velocities and the degree of angiographic vasospasm. We will also measure acute changes in neurologic exam, the need for therapeutic interventions for DCI, and new stroke on imaging at discharge. We will also measure more objective surrogate outcomes at hospital discharge and 90-day follow-up including: hospital length of stay, discharge disposition, modified Rankin Scale (mRS), and the extended Glasgow Outcome Scale (GOSE).

**Justification:** This study is not powered to detect an effect of drug administration on these endpoints, but these data will provide information for sample size calculations in larger subsequent studies.

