#### Secondary Endpoints: Blood and CSF biomarkers of drug pharmacodynamic effect

- Day 7 serum EET/DHET ratio
- Day 7 CSF EET/DHET ratio
- Day 7 CSF inflammatory cytokines
- Day 7 serum endothelial injury biomarkers
- Day 7 serum EPOME/DPOME ratio
- Day 10 serum EET/DHET ratio
- Day 10 CSF EET/DHET ratio
- Day 10 CSF inflammatory cytokines
- Day 10 serum endothelial injury biomarkers
- Day 10 serum EPOME/DPOME ratio

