#### 9.4.4 ANALYSIS OF THE SECONDARY AND TERTIARY ENDPOINTS

Secondary endpoints will be compared between the study drug and placebo groups using the per-protocol population. Serum and CSF EET/DHET ratios and biomarkers will be presented as

the mean and standard deviation, and differences evaluated with two sample Student's t-test with a two-sided type 1 error rate of 0.05%.

Tertiary endpoints will be compared descriptively between the groups based on the mean, median, standard deviation and range.

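### The rule for deeming the drug effective does not say which of four EET/DHET contrasts decides, or whether the difference must be statistically significant

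*Combined protocol and SAP*

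**What the plan says.** The justification under the secondary objective in Section 3 gives the rule: "The drug will be deemed effective if we measure higher EET/DHET ratio in the treatment group compared to placebo". It mentions no compartment, day, test or minimum difference.

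The same section defines the measurements it could refer to. For blood, "we will measure day 7 and day 10 serum EET/DHET ratios"; for CSF, "we will measure day 7 and day 10 CSF EET/DHET ratios, and compare the drug and placebo groups". Section 9.1 lists these as four separate secondary endpoints with no order among them. Shortly after the rule, Section 3 adds: "It is possible that serum EET/DHET ratio will not be measurably increased". A null serum result is thus foreseen, and the text does not say whether it would count as failure.

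Section 9.4.4 compares the secondary endpoints in the per-protocol population by a two-sample t-test "with a two-sided type 1 error rate of 0.05". A percent sign follows that figure, so the printed level is 0.0005. The section does not refer back to the rule in Section 3.

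Section 9.1 also lists the EPOME/DPOME ratio, the CSF cytokines and the endothelial markers, each on both days (for example "Day 7 serum EPOME/DPOME ratio" and "Day 7 CSF inflammatory cytokines"). No multiplicity approach is given for any of them.

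**The concern.** A rule that declares a drug effective should let two readers with the same data reach the same answer. This one does not. If serum is higher on day 7 but not on day 10, or CSF is higher and serum is not, the plan gives no way to decide whether the criterion was met. It also does not say whether a small numerical excess counts or whether the t-test must reject.

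The conclusion on drug activity could therefore rest on whichever contrast turns out favourable, under whichever criterion is adopted once the results are known. Section 4.2 calls the trial a proof of concept, so readers planning later work are likely to rely on this statement.

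**Working it through.** The plan gives no power, effect size or family-wise error figure for these endpoints, so there is no stated figure to reproduce. The check asks how often an inactive drug would satisfy the rule under each reading.

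**Inputs from the documents**
- EET/DHET contrasts: 2 compartments × 2 days = 4 (Sections 3 and 9.1).
- Test: two-sample t-test, two-sided, level printed as 0.05% (Section 9.4.4).
- Sample size: up to 30, described as equally randomised, so about 15 per arm at most (Section 4.1).
- CSF is available only from patients with an external ventricular drain (Section 8.5.1); the number is not given.

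**Assumptions**
- 5% is tried as the possibly intended level, beside the printed 0.05%.
- The four contrasts are independent or positively correlated; the documents give no correlations.
- CSF is available for either 15 or 8 patients per arm.

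**Chance per contrast under no effect**
- Numerically higher: 0.5.
- Significantly higher at two-sided 5%: 0.025.
- Significantly higher at two-sided 0.05%: 0.00025.

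**At least one of four, if independent**
- Numerically higher: 1 − 0.5⁴ = 0.9375, or 94%.
- Significant at 5%: 1 − 0.975⁴ = 0.096, or 9.6%.
- Significant at 0.05%: 1 − 0.99975⁴ = 0.0010, or 0.1%.

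**Effect of correlation.** 40,000 null trials were simulated for each setting, with 15 per arm in serum. The first figure in each cell has 15 per arm in CSF and the second has 8.

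| Correlation between days / compartments | Any numerically higher | Any significant at 5% | Any significant at 0.05% |
|---|---|---|---|
| 0 / 0 | 94% / 94% | 9.9% / 9.9% | 0.13% / 0.11% |
| 0.5 / 0 | 89% / 89% | 9.0% / 8.9% | 0.13% / 0.09% |
| 0.5 / 0.3 | 85% / 86% | 8.5% / 8.7% | 0.11% / 0.08% |
| 0.8 / 0.5 | 76% / 79% | 6.9% / 7.1% | 0.11% / 0.06% |
| 0.9 / 0.9 | 65% / 71% | 4.9% / 6.3% | 0.07% / 0.09% |

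At perfect correlation the four contrasts act as one. The numerical reading then falls to its floor of 50%, and the 5% reading to 2.5%.

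**Other readings**
- All four numerically higher: 0.5⁴ = 6.3% if independent, and up to 36% in the settings above.
- Only the two serum contrasts count: 1 − 0.975² = 4.9% at two-sided 5% if independent, and about 3.5-5% allowing for correlation.

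**One named contrast:** 50% if numerically higher is enough, 2.5% if significant at two-sided 5%, and 0.025% at the printed level.

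**The wider secondary family, as a separate matter.** Table 1 in Section 8.5.3 lists 6 CSF inflammatory markers and 5 blood endothelial markers. The count is 2 days × (1 serum EET/DHET + 1 CSF EET/DHET + 1 EPOME/DPOME + 6 + 5) = 28 tests. If they are independent, the chance of at least one false positive in either direction is 1 − 0.95²⁸ = 76% at 5%, and 1 − 0.9995²⁸ = 1.4% at the printed level. Only 4 of the 28 enter the effectiveness rule.

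**The case against.** The strongest reply is that the t-test in Section 9.4.4 is the only comparison specified for these ratios, so it is the natural meaning of a higher ratio. The sentence in Section 3 belongs to a rationale, not to the analysis section. On that view the false-positive chance is about 5-10% at 5%, and at the printed level it almost vanishes. This has force. A reader might infer from the rule that an inactive drug would usually be called effective. That needs two readings together that the documents do not state: that a numerical excess is enough, and that any one contrast will do. The wording permits this but does not require it.

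It can also be argued that the rule concerns serum alone, because the surrounding text is about systemic EETs and CSF is taken up later as a separate question. That would leave two contrasts, still without saying which day decides.

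A reader might also link the 28 secondary tests to the rule. They do not drive it, since cytokines, endothelial markers and EPOME/DPOME play no part in that sentence.

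Finally, this is a small phase 1b trial with a safety primary endpoint and a sample size based on safety. No go/no-go decision is formally attached to the rule, and full multiplicity control would be out of proportion. That is accepted. However, the synopsis labels only the tertiary endpoints exploratory, and the plan chose to state both an effectiveness criterion and formal tests. What survives is that the criterion is undefined, and that even if the t-test governs, the deciding contrast is unnamed and the level unclear.

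**Conclusion.** The point holds as one of ambiguity. Depending on the reading, the chance that an inactive drug meets the same sentence runs from about 0.1% to 94%. That spread is the defect, and it does not rest on any one correlation. The exact ranges do rest on assumed correlations and CSF numbers, and the 5-10% rests on an assumed two-sided 5% level. The documents do not support a claim that an inactive drug would usually pass.

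The lack of a multiplicity approach across the 28 secondary tests is a separate and lesser matter. Its size (76% or 1.4%, under independence) turns almost entirely on whether the printed 0.05% is intended.

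**What to change.** Before the batch assay, which Section 8.5.2 places after the last sample collection, make three changes.

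1. Replace the sentence in Section 3 with a rule that names one contrast and ties it to the test. For example: *Pharmacodynamic activity will be concluded if the serum EET/DHET ratio on study day 7 is significantly higher with GSK2256294 than with placebo, by the test and at the level in Section 9.4.4, in the per-protocol population.* Blood sampling does not depend on a drain, and Section 3 cites steady-state inhibition at 7 days. Even so, serum will not cover every randomised patient, because Section 9.3 limits the secondary analyses to those who complete 10 days of study drug. If the sponsor judges serum EET/DHET unlikely to be measurable, as Section 3 allows, it should name another single contrast instead.

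2. Confirm or correct the 0.05% in Section 9.4.4, so that both sections use one level. The choice matters for power as well. With 15 per arm and a true difference of 1 SD (an assumed value), the chance of a significantly higher result is 75% at 5% and 15% at 0.05%.

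3. Label the other 27 secondary comparisons exploratory and report them as estimates with 95% confidence intervals. No full multiplicity correction is then needed.

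The cost is a few sentences, with no added patients or samples. The downside is that the sponsor gives up choosing among contrasts after seeing the data.
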